### 7.2 List of Figures

Figure 1	Participant Flow (All participants)
Figure 2	Kaplan-Meier Curves for Primary End Point and Major Bleeding

### 7.3 List of Data Listings

#### 7.3.1 Participant Data Listings

Listing 16.2.1	Discontinued Participants
Listing 16.2.2	Protocol Deviations
Listing 16.2.4.1	Demographic Data
Listing 16.2.4.2	Baseline Characteristic Data
Listing 16.2.5.1	Compliance
Listing 16.2.5.2	Participants Who Received Study Treatment Different to Randomized Treatment

#### 7.3.2 Efficacy Data

Listing 16.2.6.1	Individual Efficacy data
------------------	--------------------------

#### 7.3.3 Adverse Events

Listing 16.2.7	All Related Adverse Events
----------------	----------------------------

**Revision History**

Version Date	File Name	Summary of Changes
1.0	PROACTXa_SAP_2020 01 15_final_clean	Original
1.1	PROACTXa_SAP_2020 04 16_v1.1	Modified the definition of the On treatment population; added the following: calculation of time in therapeutic range, details of time to event analysis, censoring rules, and assessment of model assumptions; updated the lists of tables, figures and listings
1.2	Final-SAP_2020-12-16_v1.2	Modified censoring dates, calculation of time to event for outcomes, and imputation of partially missing event dates; added the following: a sensitivity analysis for different censoring dates, the calculation of time in therapeutic range of INR before the study
1.3	PROACTXa_SAP_20221027_V1.3	Add analysis for questionnaire; modify end of study.
1.4	PROACTXa_SAP_20230111_V1.4	Modified censoring date for AT population Modified start date for primary safety outcome Modified definitions and derived variables for Quality of Life (EQ-5D-5L) Questionnaire and Duke Anticoagulation Satisfaction Scale (DASS) Modified rules to handle missing value for exploratory analysis

## Abbreviations

Abbreviation	Definition
AE	Adverse Event
AM	Arithmetic Mean
AT	As Treated
BID	Twice Daily
CI	Confidence Interval
CRF	Case Report Form
CSR	Clinical Study Report
ICF	Informed Consent Form
ICH	International Conference On Harmonization
INR	International Normalized Ratio
ITT	Intent-To-Treat
NI	Non-Inferior
NYHA	New York Heart Association
OT	On Treatment
OPC	Objective Performance Criteria
Pt-yrs	Patient-Years
SAE	Serious Adverse Event
SD	Standard Deviation
SE	Standard Error
TTR	Time in Therapeutic Range

## 1 Introduction

PROACT Xa is designed to determine if patients with an On-X aortic valve, alone or as an On-X Ascending Aortic Prosthesis, can be maintained as safely and effectively on the factor Xa inhibitor apixaban (Eliquis) as on warfarin (target INR 2-3). The primary outcome is a composite rate of valve thrombosis and valve-related thromboembolism, which will be used for co-primary analyses. The first co-primary analysis will determine whether apixaban is non-inferior to warfarin (INR target range 2.0 - 3.0) in patients with an On-X mechanical heart valve implanted in the aortic position. The second co-primary analysis will compare the composite rate for apixaban-treated patients to updated objective performance criteria (OPC) (Wu et al., 2014) for FDA-approved mechanical heart valves in the aortic position. This is an open-label study in which patients who are at least 3 months out from implantation of an On-X valve in the aortic position will be randomized in a 1:1 fashion to either apixaban 5 mg twice daily (2.5 mg twice daily in selected patients meeting reduced dose criteria) or warfarin adjusted to an INR of 2.0-3.0. Patients will be followed for at least 2 years after randomization with at least 800 patient-years (pt-yrs) of follow-up in each randomized group. If the primary efficacy hypothesis is proven, the data will be used to support a change in the On-X valve device label to state that apixaban is an acceptable alternative to warfarin for anticoagulation in patients 3 or more months after implantation of an On-X valve in the aortic position.

### 1.1 Study Objectives

#### 1.1.1 Co-Primary Efficacy Objectives

- To determine if apixaban is non-inferior to warfarin (INR target range 2.0 - 3.0) for patients with an On-X mechanical heart valve implanted in the aortic position for the primary composite outcome of valve thrombosis and valve-related thromboembolism
- To determine if apixaban provides acceptable anticoagulation for patients with an On-X mechanical heart valve implanted in the aortic position for the primary composite outcome of valve thrombosis and valve-related thromboembolism compared with an OPC

#### 1.1.2 Primary Safety Objective

- To determine if apixaban is superior to warfarin (INR target range 2.0 - 3.0) for the safety outcome of major bleeding in patients with an On-X mechanical heart valve implanted in the aortic position

#### 1.1.3 Secondary Efficacy Objectives

- To determine if apixaban is superior to warfarin (INR target range 2.0 - 3.0) for the primary composite outcome of valve thrombosis and valve-related thromboembolism in patients with an On-X mechanical heart valve implanted in the aortic position

- To compare apixaban with warfarin (INR target range 2.0 – 3.0) for the individual components of the primary outcome (valve thrombosis and valve-related thromboembolism) in patients with an On-X mechanical heart valve implanted in the aortic position
- To compare apixaban with warfarin (INR target range 2.0 - 3.0) for the primary composite outcome of valve thrombosis and valve-related thromboembolism in pre-specified subgroups of patients with an On-X mechanical heart valve implanted in the aortic position

#### 1.1.4 Exploratory Objectives

- To compare apixaban with warfarin (INR target range 2.0 – 3.0) for health-related quality of life (EQ-5D-5L) in patients with an On-X mechanical heart valve implanted in the aortic position
- To compare apixaban with warfarin (INR target range 2.0 – 3.0) for the anticoagulation satisfaction (DASS) in patients with an On-X mechanical heart valve implanted in the aortic position

### 1.2 Study Design

This is a prospective, multicenter, open-label, randomized, active controlled clinical trial to determine if patients with an On-X aortic valve, alone or as an On-X Ascending Aortic Prosthesis, can be maintained safely and effectively on apixaban. The primary outcome is a composite rate of valve thrombosis and valve-related thromboembolism, which will be used for co-primary analyses. The first co-primary analysis will determine whether apixaban is non-inferior to warfarin (INR target range 2.0 - 3.0) in patients with an On-X mechanical heart valve implanted in the aortic position. The second co-primary analysis will compare the composite rate for apixaban-treated patients to updated OPC for FDA-approved mechanical heart valves in the aortic position. Each patient will be followed for at least 2 years and each randomized arm will achieve at least 800 pt-yrs.

The study will consist of approximately 1000 patients (randomized 1:1 with approximately 500 patients in the apixaban arm and 500 patients in the warfarin arm) at a minimum of 3 sites and up to 60 sites in North America, and potentially in Europe and/or Japan, who are 18 years of age or older, at least 3 months out from an On-X aortic valve implantation, and currently managing their anticoagulation with warfarin.

Patients will be randomized to either continue warfarin or switch to apixaban. Patients randomized to apixaban will receive 5 mg twice daily (BID), or apixaban 2.5 mg BID in patients with 2 or 3 of the following characteristics:

- age  $\geq$  80 years
- weight  $\leq$  60 kilograms
- creatinine  $\geq$  1.5 mg/dL (133 micromol/L)

For patients randomized to apixaban, INR testing will be performed on the current warfarin dose with the following algorithm to initiate apixaban:

1. INR  $<$  2; stop warfarin and start apixaban

2. INR 2.0 to 3.0; hold warfarin for 2 days, start apixaban on day 3
3. INR > 3.0 to 4.0; hold warfarin for 4 days, start apixaban on day 5
4. INR > 4.0; hold warfarin for 2 days, recheck INR, refer to steps 1, 2, or 3

The procedures to be performed throughout the study are outlined in the Schedule of Activities in the study protocol (see Section 1.1 of the study protocol).

## 2 Study Populations

For purposes of analysis, the following populations are defined.

### **Intent-to-treat (ITT)**

All patients who are randomly assigned to study intervention, regardless of treatment discontinuation or switching, will be included in the intent-to-treat (ITT) population.

### **On treatment (OT)**

Patients will be censored 1 week after permanent discontinuation of the assigned treatment. All events occurring while on study drug up until 7 days of permanent discontinuation of the assigned treatment will be attributed to the randomized treatment assignment. Any event occurring when not on study drug will not be counted. All events occurring >7 days after permanent discontinuation of study drug will be censored. Patients who took the assigned treatment will be included in the corresponding treatment group until they permanently discontinue assigned treatment.

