## **5.9 Discontinuation of Study Intervention and Participant Discontinuation/Withdrawal**

For participants randomized to apixaban who develop a thrombotic or major bleeding event, the study investigator or designee will decide whether the participant should continue with apixaban, temporarily pause apixaban, or return to standard warfarin therapy. Such decisions are at the discretion of the participant's treating clinician. Participants who are returned to warfarin (section 5.8) or stop anticoagulation, regardless of whether or not they have either a thrombotic or major bleeding event, will continue to be followed in the study.

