#### 6.1.5 Time to event analysis

Unless otherwise specified in this document, time to event for the ITT population will be defined as [event date – randomization date] +1 where event occurs and as [appropriate censoring date based on analytic population – randomization date] +1 where event does not occur.

Time to event for the OT population will be defined as [event date – study drug initiation date] +1 where event occurs prior to/at 7 days after permanent study drug discontinuation and as [appropriate censoring date based on analytic population – study drug initiation date] +1 where event does not occur or occurs greater than 7 days after permanent study drug discontinuation.

Unless otherwise specified in this document, time to event for the AT population will be defined as [event date – study drug initiation date] +1 where event occurs and as [appropriate censoring date based on analytic population – study drug initiation date] +1 where event does not occur.

Treatment differences will be evaluated using a Cox proportional hazards model that includes treatment as an indicator variable and adjusted for age of valve, unless specified otherwise. The Breslow method will be used for handling ties. P-value and CI for the HR will be based on the Wald statistic. In addition, the summary tables of these analyses will include the number (%) of patients with event, Kaplan-Meier rates as well as the 95% CI by treatment monthly from randomization through the maximum follow-up. Competing risks are not taken into account for any of the Cox proportional hazards models. Competing risks may be taken into account as a sensitivity analysis if a considerable number of deaths are observed. Kaplan-Meier curves will be produced through maximum follow up available in the study, with number of patients at risk indicated below the plot at specific times.

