### 6.1.6 Censoring

In this study we expect missing outcome data to be infrequent and every effort will be made to collect all information regarding the primary outcomes through the end of the study, even in those who have discontinued the study treatment.

The censoring date for ITT analyses will be the earliest of the following: 1) most recent date of contact where the hospitalization question was assessed for the primary composite outcome or where all elements of bleeding were assessed for the primary safety outcome, including the date of a withdrawal of consent, and 2) death date (when death is not part of the outcome). Patients without any assessment of the outcome of interest will be censored at randomization.

The censoring date for AT analyses will be the earliest of the following: 1) most recent date of contact where the hospitalization question was assessed for the primary composite outcome or where all elements of bleeding were assessed for the primary safety outcome, including the date of a withdrawal of consent, and 2) death date (when death is not part of the outcome). Patients without any assessment of the outcome of interest will be censored at study drug initiation.

The censoring date for OT analysis will be the earliest of 1) most recent date of contact where the hospitalization question was assessed for the primary composite outcome or where all elements of bleeding were assessed for the primary safety outcome, including the date of a withdrawal of consent, 2) death date (when death is not part of the outcome), and 3) 7 days after the permanent discontinuation of assigned study drug. Patients without any assessment of the outcome of interest will be censored at study drug initiation.

A sensitivity analysis with the more conservative censoring date where all elements of the primary composite outcome were assessed will be performed for all three analysis populations.

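### SAP v1.4's on-treatment rule drops events in temporary interruptions while, by inference, keeping the interrupted time, and Section 6.1.5 counts those same events

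*Combined protocol and SAP*

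**What the plan says.** All SAP references are to v1.4.

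- **Section 2, On treatment (OT), events.** The definition first keeps a short tail after stopping: "All events occurring while on study drug up until 7 days of permanent discontinuation of the assigned treatment will be attributed to the randomized treatment". It then adds, without qualification: "Any event occurring when not on study drug will not be counted".
- **Section 2, On treatment (OT), time.** Only permanent discontinuation ends membership: "Patients who took the assigned treatment will be included in the corresponding treatment group until they permanently discontinue assigned treatment".
- **Section 6.1.5, Time to event analysis.** For OT, time runs to the event date "where event occurs prior to/at 7 days after permanent study drug discontinuation". It runs to the censoring date if there is no event or if the event comes later than that. Being on drug on the day of the event is not a condition.
- **Section 6.1.6, Censoring.** OT follow-up ends at the earliest of last assessed contact, death, and "7 days after the permanent discontinuation of assigned study drug". A temporary interruption is not a censoring reason.
- **Protocol Section 5.9.** Interruptions are foreseen. After a thrombotic or major bleeding event an apixaban participant may "continue with apixaban, temporarily pause apixaban, or return to standard warfarin therapy". SAP Section 6.2.3 also treats an apixaban supply gap of more than 14 days as non-compliance, not as permanent discontinuation.
- **Section 6.8.** OT is used for a sensitivity analysis of non-inferiority at the 1.75%/pt-yr margin and for one of major-bleeding superiority.

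**The concern.** An event rate is interpretable only if its numerator and denominator cover the same time. Under Section 2, an interrupted day can add person-time but never an event, so the OT rate falls below the on-drug rate. This needs no assumption that risk changes off drug. Under Section 6.1.5, the same day can contribute both. Section 6.1.5 also has no branch for an event that falls inside the window but is not counted, so two programmers following the SAP could report different OT event counts from the same data.

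An OT analysis is useful in a non-inferiority trial because switching and stopping can dilute a real difference under ITT. A rule that lowers rates, and lowers them more in the arm with more interruptions or the higher event rate, makes that cross-check less reliable.

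**Working it through.** **1. The rules side by side**

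| Event timing | Section 2 | Section 6.1.5 | Is the day in OT time (Sections 2, 6.1.6)? |
|---|---|---|---|
| On study drug | counted | counted | yes |
| During a temporary interruption | not counted | counted | yes, by inference |
| 1–7 days after permanent discontinuation | counted, if the exclusion sentence is read as limited to interruptions | counted | yes |
| More than 7 days after permanent discontinuation | not counted | not counted | no |

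The second row holds both defects: the sections disagree, and under Section 2 the time is kept without its events. No sentence states outright that interrupted days stay in. It follows because nothing in the censoring rules removes them. Section 6.3.1 divides by total patient time, but it defines that for the ITT analysis.

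**2. Reproducing the plan's figure**

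No stated figure depends on the OT rule. The sample size only anchors the illustration in step 5. Inputs from Section 6.1.8 are: both rates 1.75%/pt-yr, margin 1.75%/pt-yr, one-sided 2.5%, 90% power, 1-year accrual with half enrolled by 40% of it, 2-year minimum follow-up, and loss hazard −ln(0.95)/2 = 0.0256.

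n per arm = (1.960 + 1.282)² × [λ_W²/P_W + λ_A²/P_A] / margin², where P is the probability of an observed event. This gives 494.4 per arm, or 990 in total, as stated. With 500 per arm the power is 90.3%, as in Table 1, and the person-time is about 1,214.5 pt-yr per arm.

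**3. OT rate in one arm**

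Let λ be the on-drug rate, f the interrupted share of OT time T, and k the off-drug hazard relative to on-drug.

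- Section 2: events λ(1−f)T over time T gives λ(1−f).
- Removing both events and time: λ(1−f)T over (1−f)T gives λ.
- Section 6.1.5: [λ(1−f)T + kλfT]/T gives λ(1−f+kf).

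The mismatch bias under Section 2 is therefore −λf. The documents give neither f nor k. Assuming f = 1–5% and λ = 1.75%/pt-yr:

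- f = 1%: 1.75 × 0.01 = 0.02 (rate 1.73)
- f = 5%: 1.75 × 0.05 = 0.09 (rate 1.66)

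**4. Between-arm difference**

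The shift in (apixaban − warfarin) is −(λ_A f_A − λ_W f_W). It favours non-inferiority when λ_A f_A exceeds λ_W f_W.

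| On-drug rates, A / W | f, A / W | Difference under Section 2 | Shift |
|---|---|---|---|
| 1.75 / 1.75 | 5% / 5% | 1.6625 − 1.6625 = 0 | 0 |
| 1.75 / 1.75 | 5% / 1% | 1.6625 − 1.7325 = −0.07 | −0.07 |
| 1.75 / 1.75 | 1% / 5% | 1.7325 − 1.6625 = +0.07 | +0.07 |
| 3.50 / 1.75 | 5% / 5% | 3.325 − 1.6625 = 1.66 | −0.09 |
| 3.50 / 1.75 | 5% / 2% | 3.325 − 1.715 = 1.61 | −0.14 |

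**5. Chance of a false pass at the margin**

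This uses the Section 6.3.1 interval, on-drug rates of 3.50 and 1.75, and 1,214.5 pt-yr per arm. With matched numerator and denominator the chance of passing is 2.5%. Under Section 2 it is 2.8% (f = 2% in both arms), 3.4% (5% in both) or 4.1% (5% apixaban, 2% warfarin). A more extreme case, 10% against 2%, gives 7.2%, but it lies outside the 1–5% range. Section 6.1.3 records that the trial was stopped, so actual person-time will differ from the design value.

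**The case against.** **Retained time is an inference.** This is fair, and it is stated as one here. But Sections 2 and 6.1.6 point the same way, and no sentence removes interrupted days.

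**The 7-day tail.** A reader might infer that the exclusion sentence also cancels the tail, since a patient in it is off drug. The more natural reading is that the sentence, placed between the tail and the >7-day rule, covers temporary interruptions. Sections 6.1.5 and 6.1.6 both confirm the tail. Little hangs on it: if 5–30% of 500 patients discontinue, the tail holds 500 × 0.05 × 7/365.25 = 0.5 to 2.9 pt-yr, or 0.01–0.6 expected events at 1.75–20%/pt-yr.

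**A quarter of the margin.** At f = 5% and k = 5 the two sections give 1.66 and 1.75 × 1.20 = 2.10, a gap of 0.44, which is 25% of 1.75. That sets a one-arm gap against a margin on a between-arm difference. Only 0.09 of it is mismatch bias. The other 0.35 is off-drug hazard at an assumed fivefold rate, which is a difference in what is being estimated.

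**High-risk, unprotected days.** Being off study drug need not mean being without an anticoagulant: Section 6.2.4 tabulates non-study warfarin. For bleeding, a higher risk off drug cannot be presumed. In addition, Section 6.3.1 counts patients with an outcome, so someone paused after a qualifying event is already counted. Only some pauses can lose a countable event.

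**Sensitivity only.** This stands. OT in Section 6.8 is one of three listed non-inferiority sensitivity analyses, and success is declared on ITT.

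**Conclusion.** The point holds as an internal inconsistency with a small bias of known form. An event in a temporary interruption is excluded by Section 2 and counted by Section 6.1.5. Under Section 2 each arm's OT rate is multiplied by (1−f).

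At 1.75%/pt-yr and an assumed f of 1–5%, that is 0.02–0.09%/pt-yr per arm. With equal rates, the difference is unchanged if pauses are balanced. It shifts by −0.07%/pt-yr, or 4% of the margin (0.07/1.75), at 5% against 1% paused. The shift favours non-inferiority when apixaban is worse or is paused more, and it can go the other way if warfarin is interrupted enough more. Protocol Section 5.9 describes pauses for apixaban specifically, so balance cannot be presumed, but no document gives the actual shares.

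Only the OT sensitivity analyses of non-inferiority and major bleeding are touched. A reader might infer that the trial's conclusion is at risk; the documents do not support that. The ITT co-primary tests, the AT primary safety test, the margin and the sample size do not depend on this rule. It is worth correcting because the SAP does not currently define one OT event count.

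**What to change.** Use one matched rule in SAP Sections 2, 6.1.5 and 6.1.6. Either option is coherent:

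1. Delete the sentence "Any event occurring when not on study drug will not be counted". Events and time then both run to 7 days after permanent discontinuation, as Sections 6.1.5 and 6.1.6 already say. The cost is one sentence and no new data. The OT analysis would then include off-drug events during pauses, which may not be what Section 2 intended.
2. Where interruption dates are available, exclude both the events and the days of each interruption beyond the same 7-day lag, and amend Sections 6.1.5 and 6.1.6 to match. This is closer to a true on-drug rate but needs start and stop dates. The protocol's Schedule of Activities has monthly calls to assess gaps and dosing changes, which may supply some of them.

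If the sentence is kept, state that it does not apply to the 7-day tail. In either case, reconcile the definition with protocol Section 8.3, whose OT population is censored 1 week after anticoagulant switching or discontinuation and has no such exclusion sentence. Because v1.4 records that the trial has been stopped, date and justify the change. If outcome data have already been examined, report OT results under both event rules.

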### **As treated (AT)**

All patients randomly assigned to study intervention and who take at least 1 dose of study intervention. Patients will be analyzed according to the intervention they initially received. For example, if a patient was randomized to apixaban, took 1 dose of apixaban and then switched to non-study warfarin, this patient will be included in the apixaban arm for the as treated (AT) population.

### 3 Definitions and Derived Variables

#### 3.1 Valve thrombosis

Valve thrombosis is defined as any thrombus not caused by infection attached to or near an implanted On-X valve that occludes part of the blood flow path, interferes with valve function, or is sufficiently large to warrant treatment other than continued oral anticoagulation. Furthermore, valve thrombus found at autopsy in a patient whose cause of death was not valve related or found at operation for an unrelated indication will also be reported as valve thrombosis .(Akins et al., 2008)

